The primary likely benefit of this novel therapeutic strategy is avoiding the side effects of systemic antibiotics that cause significant additional morbidity and medical expense. Other possible benefits of this novel strategy are improved wound healing time and less scar formation. This work will capitalize on the polymer structure of TheraGauze that provides a platform for fluid redistribution within the wound bed without causing skin maceration (Landsman 2008). We have developed an antimicrobial form of TheraGauze by loading TheraGauze with tobramycin (TheraGauze+tobramycin). Prior in vitro testing demonstrated potent and sustained antibacterial activity for TheraGauze+tobramycin against a wide range of bacterial pathogens, including all strains of community-associated MRSA tested (Echague, Hair et al. 2010). Lack of systemic absorption is a well-established property of tobramycin. Thus, high concentrations can be delivered locally in the wound greatly exceeding typical minimum inhibitory concentrations (MICs) without concern for systemic toxicity. Additionally, tobramycin is a highly bactericidal antimicrobial compound. Tobramycin is rarely used as a systemic antibiotic now having been largely replaced by fluoroquinolones. Therefore, selective pressure that could promote development of antibiotic resistance and compromise systemic antibiotic therapy is not a concern.

Tobramycin has been used for many years both as topical therapy applied to the eyes as well as in surgical wounds as tobramycin-containing polymethacrylate beads. Topical application of tobramycin to cutaneous wounds has also been reported without evidence of local or systemic toxicity. Andrew et al reported application of 3% (w/v) tobramycin with dexamethasone (i.e., Tobradex) ointment applied to post dermatological procedure surgical wounds twice-a-day for 2 weeks. Eighteen human subjects were enrolled and no local or systemic side effects were noted (Andrew, Luecke et al. 2012)

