In 2003 Simplex P with tobramycin was the first FDA approved antibiotic impregnated bone cement ([www.stryker.com](http://www.stryker.com)). Preparations of tobramycin-impregnated bone cement appear to generally range from 1g to 1.2g in 20 ml (50 – 60 mg/ml) (Sterling, Crawford et al. 2003, McLaren, McLaren et al. 2008). Tobramycin is reported to be the antibiotic of choice for bone cement for more than 75% of orthopedic surgeons (Fish, Hoffman et al. 1992) with excellent local tobramycin levels and minimal systemic tobramycin levels (Soto-Hall, Saenz et al. 1983, Eckman, Henry et al. 1988, Davies and Harris 1991, Pritchett and Bortel 1992, Brien, Salvati et al. 1993, Sterling, Crawford et al. 2003, McKee, Li-Bland et al. 2010). Despite the extensive literature on tobramycin bone cement there are no mentions of local toxicity. It is notable that so little toxicity has been reported given the significantly varying amounts of tobramycin cement are used for different types of orthopedic procedures and depending on the amount of bone being replaced. The wounds the tobramycin cement are in deep tissue spaces that are highly vascular. In contrast, TheraGauze/tobramycin will be placed into small (2 - 10ml) cutaneous abscesses where the bacterial infection has been walled off to protect the body from spread.

Tobramycin has also been used as a topical ophthalmic preparation for many years both as an ointment and drops (3 mg/ml) (e.g., Tobrex). Despite the very sensitive nature of topical application to the eye the package insert for Tobrex notes <1% hypersensitivity and eye or eyelid irritation is 3%, which is a typical rate for antibiotic eye drops. Additionally, Tobramycin eye drops (3 mg/ml) have been shown to have no adverse effects on reepithelialization and be well tolerated after penetrating keratoplasty (Blavin, Sauer et al. 2012)

Thus, there are several decades of human data demonstrating the safety of tobramycin when used topically for cutaneous and ocular wounds and in surgical wounds. The data suggests that local or systemic toxicity is extremely rare when tobramycin is used in these ways.

**Primary Endpoint.** The primary endpoint of the study is to evaluate the safety of and identify side effects of TheraGauze/tobramycin wound packing compared with standard of care management for cutaneous abscesses requiring incision and drainage.

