## Methods.

### Design:

This is a proof-of-concept, prospective, randomized clinical trial for safety of TheraGauze-tobramycin in adult subjects who present to Emergency Department settings for care of skin abscess requiring incision and drainage. A control, standard of care, arm is included to provide some data with respect to the side effect profile of current furunculosis management for comparison.

Two arms are proposed for this study:

1. Incision + TheraGauze+tobramycin packing (no systemic antibiotics)
2. Incision + standard iodoform wick or plain cotton wick packing ( $\pm$  p.o. antibiotics)

Anti-microbial TheraGauze (saturated with tobramycin ophthalmic solution at 3 mg/ml) will be packed into the drained wounds of the subjects in the study arm. The control arm will receive current standard of care wound packing with a choice of iodoform wick or plain cotton wick, based on the preference of the ED physician. After packing, the wound excess TheraGauze or wick will be cut away. The ED physicians have the option to prescribe an oral antibiotic or not,

according to their preference. The following oral antibiotic choices are available for subjects in the control arm only:

- Bactrim (TMP/SMX)
- Vibramycin (doxycycline)
- Cleocin (clindamycin)

Antibiotics will be purchased by subjects from their local pharmacy.

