#### **STATISTICAL ANALYSIS PLAN**

The research coordinators will collect data on a hard copy source document. Clinical and laboratory data will then be entered into an Access database by the coordinator and lab personnel.

The data will be analyzed using SAS 9.4 software. All statistical tests will be two-sided with a significance level of 0.05. Patients who withdraw while on treatment will be included in the data analysis for each time point before withdrawal. Baseline and follow-up measurements of safety, tolerability, numbers of pathogenic bacteria, wound infection persistence or worsening, and gross effects on the rate of wound healing will be summarized using descriptive statistics such as mean, median, standard deviation, interquartile range, frequency, and percentage where appropriate. Normality assessments for the continuous variables will be completed using Shapiro-Wilk tests and stem-and-leaf plots.

Tests of equivalence between the TheraGauze + tobramycin and standard iodoform wick packing treatment groups will establish statistical significance if the two-sided 90% confidence

interval for the difference falls within the limits  $(-\delta, \delta)$ , where  $\delta$  is the margin of clinically accepted difference. This analysis will determine whether the outcomes are equivalent between the TheraGauze+tobramycin and standard iodoform wick packing treatment groups.

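### The plan's only between-arm test is a symmetric equivalence rule with no numeric margin, named outcome or interval method; if it covers side effects, it cannot tell a reduction from an increase

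*Combined protocol and SAP*

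**What the plan says.** The Statistical Analysis Plan first lists what will be summarised descriptively: "Baseline and follow-up measurements of safety, tolerability, numbers of pathogenic bacteria, wound infection persistence or worsening", and effects on healing. A separate paragraph gives the only between-arm rule. Equivalence is concluded when the two-sided 90% interval for the difference falls within (-δ, δ), where δ "is the margin of clinically accepted difference". No number, scale, outcome, time point or interval method follows. The paragraph ends: "This analysis will determine whether the outcomes are equivalent between the TheraGauze+tobramycin and standard iodoform wick packing treatment groups".

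The general sentence on two-sided 0.05 tests names no other comparison. The Research Monitor's look for superiority or inferiority is a chart review without a statistical rule.

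Three other statements bear on the point:

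- The primary endpoint is to "evaluate the safety of and identify side effects of TheraGauze/tobramycin wound packing compared with standard of care management".
- The Design section says the control "arm is included to provide some data with respect to the side effect profile of current furunculosis management for comparison".
- The Background expects a direction: "The primary likely benefit of this novel therapeutic strategy is avoiding the side effects of systemic antibiotics".

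The Design section defines the control arm as "Incision + standard iodoform wick or plain cotton wick packing", with or without oral antibiotics. The equivalence paragraph names only iodoform.

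**The concern.** An equivalence rule asks whether a difference is small in either direction. That is a sensible question for infection or healing, where the aim may be to do about as well as standard care. For side effects, the protocol hopes for fewer on TheraGauze and needs to know whether there are more. A symmetric rule gives both the same result, equivalence not shown, and can give it for a reduction even when the same interval excludes a harm of size δ.

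Two further gaps apply whatever the outcome. About 50 completers may be too few for the rule to determine anything. And because δ and the interval method are open, the result depends on choices still to be made.

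**Working it through.** **The plan's own figures.** Study Size gives 100 randomized, 2:1 allocation and 50% retention: 100 × 0.50 = 50 completers, as stated. Two thirds of 100 is about 67, giving 67:33 randomized. Two thirds of 50 is about 33, giving 33:17 completing if retention is equal by arm. The plan also says: "Patients who withdraw while on treatment will be included in the data analysis for each time point before withdrawal". The analysed number may therefore lie between these two cases. A 90% interval leaves (1 - 0.90)/2 = 5% on each side. No power, target difference or derivation of N = 100 is given.

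**Assumptions.** The documents give neither δ nor side-effect rates by arm. The one relevant rate is diarrhea at about 20% on oral antibiotics (Background). I use it as an illustrative control rate and vary the rest.

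**Formulas.** With d = p1 - p2 (TheraGauze minus control):

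- Wald limits: d ± 1.645 × √[p1(1-p1)/n1 + p2(1-p2)/n2].
- Newcombe limits, with (l, u) each arm's Wilson limits: lower = d - √[(p1-l1)² + (u2-p2)²]; upper = d + √[(u1-p1)² + (p2-l2)²].
- Pass = lower > -δ and upper < δ. Harm excluded = upper < δ.
- Probabilities are exact sums over all pairs of event counts from two independent binomials.

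**One case by hand.** For 67:33 and 10% v 20%, the standard error is √(0.09/67 + 0.16/33) = √0.00619 = 0.0787, so the half-width is 1.645 × 0.0787 = 0.129. Centred on the true difference, the interval runs from -0.229 to +0.029. With δ = 0.20 it fails on the favourable side only.

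**Results at δ = 0.20 (Wald / Newcombe).**

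| Arms | TheraGauze v control | Passes | 20-point harm excluded |
|---|---|---|---|
| 67:33 | 20% v 20% | 53% / 55% | 79% / 83% |
| 67:33 | 10% v 20% | 37% / 32% | 99.5% / 99.7% |
| 67:33 | 20% v 10% | 38% / 44% | 39% / 46% |
| 670:330 | 10% v 20% | 98.8% / 98.7% | 100% / 100% |
| 33:17 | 20% v 20% | 11.8% / 6.5% | 55% / 59% |
| 33:17 | 10% v 20% | 20.7% / 13.9% | 93.5% / 93.2% |

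At 67:33, halving and doubling pass about equally often, although the first all but rules out harm and the second does not. The 670:330 row shows the cause: an off-centre true difference combined with a small sample. At 33:17 imprecision dominates and the pattern reverses, with the reduction passing more often than no effect.

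**A single data set.** 3/67 v 7/33 gives 4.5% - 21.2% = -16.7 points, Wald 90% interval -29.2 to -4.3. It lies wholly in TheraGauze's favour, yet equivalence fails for any δ up to 29 points.

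**Can the rule determine equivalence?** With 33:17 and equal 20% rates, the half-width is 1.645 × √(0.16/33 + 0.16/17) = 0.196, wider than a δ of 0.15. The rule passes 0.3% / 0% of the time (67:33: 12% / 11%).

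**Does the interval method matter?** With 33:17, equal 2% rates and δ = 0.10, Wald passes 61% and Newcombe 0%. With no events in either arm, the Wald interval has zero width, while Newcombe runs from -13.7 to +7.6 points.

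**The case against.** The strongest reply is that the rule may not apply to side effects. Safety and tolerability appear in the descriptive sentence, the equivalence paragraph says only outcomes, and a control arm meant to give some data for comparison can be served descriptively. This stands as far as it goes: coverage of side effects is a reading. It is the likelier one, because otherwise the primary endpoint has no between-arm inference, in which case the plan should say so.

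A reader might also infer that the rule fails because of the direction of effect and not through imprecision. The calculations do not support that. With ten times the patients, the 10% v 20% case passes about 99% of the time. Only a true reduction at or beyond δ keeps failing, and there non-equivalence is the correct answer. At the protocol's own completer count and δ = 0.20, the reduction passes more often than no effect. The pattern reappears at 33:17 with δ = 0.30 (10% v 20% passes 56% / 51%, 20% v 20% passes 63% / 65%), but that margin exceeds the whole assumed control rate.

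The 20% rate may be too high, since antibiotics are optional in the control arm. At 67:33 and δ = 0.20, 5% v 10% passes 77% / 67% against 85% / 82% for 10% v 10%, a more modest penalty.

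Finally, this is a Phase I pilot, no decision is tied to the result, and the interval itself shows direction. That limits the consequence but does not supply the missing elements.

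**Conclusion.** The concern holds in two parts, with different confidence.

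High confidence: the only between-arm inference has no numeric margin, outcome or interval method, and the promise to determine equivalence is unsupported at about 50 completers for narrow margins (0.3% / 0% at equal 20% rates and δ = 0.15). With rare events the method alone can decide the result (61% v 0%).

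Moderate confidence: if the rule covers side effects, its result cannot distinguish the hoped-for reduction from an increase. At 67:33 and δ = 0.20 the two pass 37% / 32% and 38% / 44% of the time, with harm excluded over 99% in one case and 39% / 46% in the other. This rests on assumed rates and margins and on the reading of the outcome. It does not show that a reduction generally lowers the chance of passing, or that the trial would reach a wrong safety decision. The descriptive summaries remain usable, and similarity is a reasonable question for infection outcomes. The plan should be changed before analysis.

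**What to change.** For side effects, replace the equivalence test and its closing promise with estimation. Suggested wording:

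> The proportion of subjects reporting any of diarrhea or loose stool, nausea or vomiting, abdominal discomfort, rash, headache, dizziness, drowsiness or thrush at any post-treatment contact through Visit 3 will be compared as a risk difference (TheraGauze minus the whole control arm, iodoform or plain cotton wick, with or without oral antibiotics), with a two-sided 95% Newcombe interval and no equivalence conclusion. Local-site reactions will be reported with equal prominence in the same format; a rash at the wound site counts there only. The analysis includes all randomized subjects with at least one post-treatment contact, by assigned arm. The number with no contact will be reported by arm.

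These symptoms are asked of both arms by phone and at Visits 2 and 3. The phone item on side effects among those who took antibiotics should not be used, because the TheraGauze arm is assigned none.

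State the expected 95% half-widths at common rates of 5%, 20% and 50%: about 17, 23 and 26 points at 33:17, and about 11, 16 and 20 at 67:33.

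If equivalence is kept for infection, bacterial or healing outcomes, name each outcome, its numeric margin and the interval method before arm-level outcome data are seen. The timing matters because the principal investigator has database access (Confidentiality) and performs most Visit 3 assessments (Roles of Research Team Members). Correct the comparator label to the full control arm.

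The cost is plan wording and one outcome built from items already collected. The sponsor gives up an equivalence claim for side effects and must report wide intervals. Supplying δ, outcome and method alone would cure the missing detail, but not the symmetric shape if the rule is applied to side effects.

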#### **CONFIDENTIALITY.**

Subjects' research charts will be maintained in the locked coordinators offices until each subject completes the study. Electronic data will be in an encrypted password-protected database, accessible only to the study coordinators, biostatistician, and PI. Subjects' research charts and laboratory specimens will be stored until the completion of the study. Research charts will be maintained in a secured facility for the length of time mandated by federal law. Laboratory specimens (i.e. bacterial culture isolates) will be destroyed at the completion of the study.

#### **AMENDMENTS.**

Any changes in procedures will be approved by the IRB prior to implementation, except for those necessary for subject safety. Deviations that change the risk/benefit ratio will be reported to the IRB.

#### **ROLES OF RESEARCH TEAM MEMBERS**

Physician investigators and Emergency Room staff will identify potential subjects and will notify the coordinator. The coordinator will explain the study and she or the physician will obtain informed consent. The physician will collect medical history culture the wound, and care for the wound per standard of care, using TheraGauze with tobramycin or standard gauze per randomization. The coordinators will ensure that all data are collected and recorded in the study chart, collect lab results, schedule follow-up appointments and make telephone contacts. Routine cultures and sensitivities will be performed in the hospital laboratories. The research lab staff will perform quantitative analysis. Coordinators and lab staff will enter data into the database. The statistician, with the PI, will analyze the results. The PI will oversee all of the above activities as well as performing most of the Visit 3 clinical assessments. and report findings to the sponsor.

#### **RESEARCH MONITOR.**

All Serious Adverse Event (SAE) reports will be sent to the Research Monitor, [name], within 24 hours. The Research Monitor will also review subject charts for safety on a 3 to 6 month basis, assessing for evidence of tolerability or superiority/inferiority between the arms, and will discuss her findings with the PI. The Research Monitor may discuss the protocol with the investigators, interview subjects, and consult with others outside the study about the research. She shall have the authority to stop the protocol, remove subjects from the protocol, and take any necessary steps to protect the safety and well-being of subjects until the IRB can assess the Monitor's report. The Research Monitor shall have the responsibility to promptly report her observations and findings to the IRB or other designated official. The Research Monitor is required to review all unanticipated problems involving risks to subjects or others, serious adverse events and all subject deaths associated with the protocol and provide an unbiased written report of the event. At a minimum, the research monitor must comment on the outcomes of the event or problem and in the case of a serious adverse event or death, comment on the relationship to participation in the study. The research monitor must also indicate whether he/she concurs with the details of the report provided by the principal

investigator. Reports for events determined by either the investigator or research monitor to be possibly or definitely related to participation and report of events resulting in death must be promptly forwarded to the USAMRMC ORP HRPO.

Study Visit Schedule:

PROCEDURE	VISIT 1	VISIT 2	VISIT 3
	Screening/Day 1	Day 3-1/+2 days	Day 7±2 days
Consent	X		
Inclusion/exclusion	X		
Demographics	X		
Medical history	X		
History and current symptoms	X	X	X
Temperature, wound assessment	X	X	X
Culture abscess	X	X	
Randomization	X		
Apply wick	X		
Provide prescription if applicable	X		
Remove packing (if applicable)			
Follow-up phone call Day 2 (+2)	X		
Follow-up phone call day prior to Day 7 visit		X	

REFERENCES

Andrew, R., G. Luecke, S. Dozier and D. G. Diven (2012). "A pilot study to investigate the efficacy of tobramycin-dexamethasone ointment in promoting wound healing." *Dermatol Ther (Heidelb)* **2**(1): 12.

Bell, T. L., J. N. Foster and M. L. Townsend "Trimethoprim-sulfamethoxazole-induced hepatotoxicity in a pediatric patient." *Pharmacotherapy* **30**(5): 539.

